5.17. Subgroup Analyses

A subgroup analysis will be performed on the primary endpoint using the treatment regimen estimand with the washout method for multiple imputation for missing data, and the same model as the primary analysis model by adding 3-way interaction of visit-by-treatment-by-subgroup, 2-way interaction of treatment-by-subgroup, and visit-by-subgroup. The 2-way interaction of treatment-by-subgroup at the primary time point of 26 weeks will be evaluated to assess an interaction in the treatment effect with the subgroup levels. Significance will be evaluated at 2-sided alpha of 0.1. The following are candidate subgroups that might be analyzed. This list is not necessarily all-inclusive:

- gender
- age group (≤ 14 years old, > 14 years old)
- race
- ethnicity
- region (US and non-US)
- duration of diabetes at baseline ($<$ median duration and \geq median duration)
- baseline BMI ($<$ median and \geq median)
- baseline body weight ($<$ median and \geq median)
- metformin usage (“yes” or “no”)
- baseline HbA1c ($\leq 8.0\%$, $> 8.0\%$)
- basal insulin usage (“yes” or “no”)
- monotherapy (“yes” or “no”)
- metformin and insulin usage (“yes” or “no”)

A descriptive summary of the change from baseline to Week 26 in HbA1c, FBG, and BMI, and HbA1c target of <7% at Week 26 will be presented by age group, categorized by (10 to 14 years) and (>14 years).

A descriptive summary for the key clinically important safety endpoints may be presented for the aforementioned age group.

5.18. Patient-Reported Outcome Analyses

All PRO analyses are exploratory. Demographic and baseline characteristics of the pediatric population at baseline for HO population will be summarized. The EQ-5D-Y is a standardized generic measure of health status developed by the EuroQol Group. The EQ-5D-Y consists of the EQ-5D-Y descriptive system and the EQ VAS. The descriptive system comprises the same 5 dimensions as the EQ-5D 3 level (EQ-5D-3L), but using a child-friendly wording (mobility; looking after myself; doing usual activities; having pain or discomfort; and feeling worried, sad, or unhappy). Each dimension has 3 levels: no problems, some problems, or a lot of problems. The EQ VAS records the respondent's self-rated health on a vertical VAS where the endpoints are labelled "The best health you can imagine" and "The worst health you can imagine." This VAS information can be used as a quantitative measure of the perception of their overall health by the individual respondents.

The EQ-5D-Y health states, defined by the EQ-5D descriptive system, will be converted into a single index value by applying a formula that essentially attaches value (also called weights) to each of the levels in each dimension. However, as of 2020, an EQ-5D-Y index formula is not available for converting the health states into a single index value. The analysis for the PRO measures (EQ-5D-Y VAS and EQ-5D-Y index scores only if available) will be MMRM for the change in PRO score from baseline to each postdose visit for the HO population. The MMRM will include treatment, insulin usage, metformin usage, baseline HbA1c stratification, visit, visit-by-treatment interaction as fixed effects, and baseline score as a covariate. The variance-covariance structure for this model will be selected in the same order defined in Section 5.2. The EQ-5D-Y index score will be analyzed if it is available. Patient responses by EQ-5D-Y domains (mobility; looking after myself; doing usual activities; having pain or discomfort; feeling worried, sad, or unhappy) will also be descriptively examined. The above analyses will be calculated and reported for Age <13 years old, ≥ 13 years old, and ≤ 14 years old, >14 years old, and all age combined group. Please refer to the EQ-5D-Y User's Manual for appropriate descriptive reporting examples, VAS, and how to handle missing data.

The 23-item PedsQL Generic Core Scales were designed to measure the core dimensions of health as delineated by the World Health Organization, as well as role (school) functioning. The 2 versions used are for children (ages 8 to 12) and for teens (ages 13 to 18). The generic scale comprises 4 multidimensional scales and 2 Summary Scores along with scores calculated for each of the 4 dimensions and a total score. The 4 dimensional scales are Physical Functioning (8 items), Emotional Functioning (5 items), Social Functioning (5 items), School Functioning (5 items), and the 2 Summary Scores, which are Psychosocial Health Summary Score (15 items),

and Physical Health Summary Score (8 items), and a Total Score (23 items). Higher scores indicate better health-related quality of life (HRQOL).

The PEDS-QL 3.2 Diabetes Module is a diabetes-specific HRQOL measurement instrument that includes 33 items comprising 5 dimensions for ages 13 to 45 years. For ages 2 to 12 years, the PedsQL 3.2 Diabetes Module is composed of 32 items comprising 5 dimensions (1 less item for the Worry Scale). The 5 dimensions of this diabetes specific module are Diabetes (15 items), Treatment I (5 items), Treatment II (6 items), Worry 2 items (3 items for teens and adults), and Communication (4 items). Scores are calculated for each of the 5 dimensions and a total score is available. Higher scores indicate lower problems.

For the PEDS-QL generic and diabetes scales transformation of scores are needed as indicated by the scoring manual. Items are scored on a 5-point Likert scale from 0 (Never) to 4 (Almost always). Items are then reversed scored as follows: 0=100, 1=75, 2=50, 3=25, 4=0. The dimension scores and the summary scores are calculated by summing the transformed scores of the items divided by the number of items answered. Moreover, for both the PEDS-QL generic and diabetes scales, if more than 50% of the items in the scale are missing, then the Scale Scores should not be computed. If 50% or more items are completed, mean of the completed items in a scale will be used to impute the missing scores. Refer to the PEDS-QL scoring manual to appropriately score all the dimensions, subscales (for example, Psychosocial Health Summary Score, Physical Health Summary Score for the generic version), and total scores.

The PEDS-QL Diabetes [3.2] Worry Dimension will be analyzed via an MMRM for the change in score from baseline to Week 26 and Week 52 in HO population. The model will include treatment, insulin usage, metformin usage, baseline HbA1c stratification, visit, and visit-by-treatment interaction as fixed effects and baseline score as a covariate. The variance-covariance structure for this model will be selected in the same order defined in Section 5.2. Baseline data and each postdose visit scores for the Worry Dimension will be calculated and reported for Age <13 years old, ≥ 13 years old, and ≤ 14 years old, > 14 years old, and all age combined group.

The analysis for the PRO measures (PEDS-QL Diabetes [3.2] [except Worry Dimension as it is already specified above] and PEDS-QL [generic scale]) will use similar MMRM model to that for PEDS-QL worry dimension score. The analyses will cover the total scores, all subscale scores, and dimensions. Baseline data and each visit scores will be calculated and reported for Age <13 years old, ≥ 13 years old, and ≤ 14 years old, > 14 years old, and all age combined group.

Details about scoring the PRO instruments can be found in the Peds-QL Scoring Manual (Mapi Research Trust 2015 [WWW]) and EQ-5D-Y User Guide (EuroQol Research Foundation 2015 [WWW]).

6. Unblinding Plan

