10.2. Health Outcome/Quality of Life Measure

The questionnaire will be administered by the investigator according to the study schedule in countries where the questionnaire has been translated into the native language of the region and linguistically validated.

EQ-5D-Youth Version

The EQ-5D is a standardized generic measure of health status developed by the EuroQol Group. The EQ-5D-Y consists of the EQ-5D-Y descriptive system and the EQ VAS. The descriptive system comprises the same 5 dimensions as the EQ-5D 3 level (EQ-5D-3L), but using a child-friendly wording (mobility; looking after myself; doing usual activities; having pain or discomfort; and feeling worried, sad or unhappy). Each dimension has 3 levels: no problems, some problems, or a lot of problems. The EQ VAS records the respondent's self-rated health on a vertical, EQ VAS where the endpoints are labeled, "The best health you can imagine," and, "The worst health you can imagine." This VAS information can be used as a quantitative measure of the perception of their overall health by the individual respondents.

The EQ-5D-Y will be administered at baseline, Week 26, and Week 52 (or early termination [ET]), as per the Study Schedule ([Attachment 1](#)). The Week 26 and Week 52 EQ-5D-Y is an objective in the study.

Details about scoring the PRO instrument can be found in the EQ-5D-Y User Guide (www.euroqol.org).

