4.3. Exploratory Objectives

The exploratory objectives are to compare the dulaglutide 0.75 mg and dulaglutide 1.5 mg arms (individually and pooled) to placebo with respect to the following parameters at 26 weeks, and to assess the following parameters in the dulaglutide 0.75 mg and dulaglutide 1.5 mg arms (individually and pooled) at Week 52 (unless otherwise specified):

- Percentage of patients with HbA1c $\leq 6.5\%$ at Weeks 26 and 52
- Change in HbA1c between baseline and Week 13
- Percentage of patients having HbA1c $\leq 6.5\%$ without severe, documented symptomatic (<70 mg/dL), or probable hypoglycemic episodes at Weeks 26 and 52
- Percentage of patients having HbA1c $< 7.0\%$ without severe, documented symptomatic (<70 mg/dL), or probable hypoglycemic episodes at Weeks 26 and 52
- Change in weight between baseline and Weeks 26 and 52
- Change in hormone-related safety assessed by the effect on morning serum prolactin, insulin-like growth factor-1 (IGF-1), estradiol, testosterone (males only), luteinizing hormone (LH), and cortisol between baseline and Weeks 26 and 52
- Change in serum lipids between baseline and Weeks 26 and 52
- Change in Tanner staging between baseline and Weeks 26 and 52
- Change in BMI standard deviation score (SDS) between baseline and Weeks 26 and 52
- Change in height and height SDS between baseline and Weeks 26 and 52
- Change in waist circumference between baseline and Weeks 26 and 52
- Change in the EQ-5D-Youth version (EQ-5D-Y) visual analogue scale (VAS) score between baseline and Weeks 26 and 52
- Percentage of patients reporting each level of problem on each dimension of the EQ-5D-Y at baseline and Weeks 26 and 52
- Assess effect of dulaglutide on measures of insulin resistance, beta cell function, and serum adiponectin at Weeks 13 and 26

- Change in basal insulin dose from baseline to Week 26 and from baseline to Week 52

5. A Priori Statistical Methods

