5.4. Patient Population

The following patient populations described in [Table GBGC.5.1](#) will be used to analyze the data.

Table GBGC.5.1. Analysis Populations for Study H9X-MC-GBGC

Population	Definition
All Entered	All patients who signed an informed consent
All Randomized	All patients who were randomized to a treatment arm as planned
Nonrandomized	All patients who entered, but were not randomized to a treatment arm
ITT	All randomized patients who took at least 1 dose of the study medication for an assigned treatment arm. For EMA, patients treated with diet and exercise alone who have not previously received metformin will be excluded from the ITT population for the primary analysis related to the primary endpoint (HbA1c) change from baseline to Week 26.
PP	All ITT population patients who have met the following criteria: 
 • Have no important protocol deviations (Section 5.7) expected to influence the assessment of the primary objective • Have an overall compliance of at least 75% up to Week 26 • Have completed the double-blinded period (26 weeks therapy [Visit 9]) with nonmissing HbA1c for both the Week 26 and baseline visits
HO	A subset of the ITT population who signed an informed consent for the HO addendum and completed testing on at least 1 occasion.

Abbreviations: EMA = European Medicines Agency; HbA1c = hemoglobin A1c; HO = health outcomes;

ITT = intent-to-treat; PP = per protocol.

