5.16. Exploratory Analysis

The population for all exploratory analyses is the ITT population, which treats all postrescue therapy measurements as missing (efficacy estimand) with all scheduled postdose visit data up to Week 52 (Visit 16) unless otherwise stated.

5.16.1. *Parameters of Interest*

The exploratory parameters of interest include, but are not limited to, the following measurements in change from baseline to Week 26 and 52 (unless otherwise specified):

- HbA1c to Week 13 (Visit 6)
- Percentage of patients reaching HbA1c target of:
 - $\leq 6.5\%$
 - $\leq 6.5\%$ without severe, documented symptomatic (blood glucose [BG] <70 mg/dL), or probable hypoglycemic episodes
 - $<7.0\%$ without severe, documented symptomatic (BG <70 mg/dL), or probable hypoglycemic episodes
- Body weight
- BMI standard deviation score (SDS)
- Height and height SDS
- Waist circumference
- Measures of insulin resistance, beta cell function, and serum adiponectin at Weeks 13 and 26

- Change in basal insulin dose from baseline to Week 26 and from baseline to Week 52

5.16.2. *Analysis on HbA1c Change from Baseline to Week 13*

The same MMRM model as that described in Section 5.11.1 will be used. The Week 13 data will be included in the analysis of the data through Week 26 and through Week 52.

5.16.3. *Analysis of Percentage of Patients Reaching HbA1c Target*

The same model as that described in Section 5.12.1 for the percentage of patients reaching a HbA1c target of <7% will be applied for 3 parameters of interests: HbA1c \leq 6.5%, composite endpoint of HbA1c <7% without severe, documented symptomatic (BG <70 mg/dL), or probable hypoglycemic episodes, and HbA1c \leq 6.5% without severe, documented symptomatic (BG <70 mg/dL), or probable hypoglycemic episodes. Detailed hypoglycemia episodes are defined in Section 5.15.2.1.

Additional analysis will be performed on the ITT population using logistic regression defined in Section 5.12.2 for Week 26 and Week 52, where patients who have been rescued or have missing data at Week 26 or Week 52 will be imputed to have not achieved the target, while for nonrescued patients the available data will be used.

5.16.4. *Analysis of Change in Body Weight, BMI SDS, Height and Waist Circumference*

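### The EQ-5D-Y VAS model is restricted to patients who signed the health-outcomes addendum, although the main protocol collects EQ-5D-Y study-wide; the population for the EQ-5D-Y dimension summaries is not named.

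*SAP*

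**What the plan says.** **Collection.** EQ-5D-Y is a main-study procedure. Protocol 10.2 states: "The EQ-5D-Y will be administered at baseline, Week 26, and Week 52 (or early termination [ET]), as per the Study Schedule". Protocol 7.1 lists it among the ordinary procedures at the Week 0, 26 and 52 visits, and Attachment 1 carries it in the main schedule. The only limit stated is that it is given "in countries where the questionnaire has been translated into the native language of the region and linguistically validated".

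**Objectives.** Protocol 6.3 and SAP 4.3 list two EQ-5D-Y objectives, neither confined to a subset. One is "Change in the EQ-5D-Youth version (EQ-5D-Y) visual analogue scale (VAS) score between baseline and Weeks 26 and 52". The other is the percentage of patients at each problem level on each dimension at baseline, Week 26 and Week 52.

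**Default population.** SAP 5.16 says: "The population for all exploratory analyses is the ITT population, which treats all postrescue therapy measurements as missing (efficacy estimand"). The sentence goes on to allow exceptions where the plan states otherwise.

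**Population actually used.** SAP 5.18 says "All PRO analyses are exploratory", and then that the VAS and index analysis "will be MMRM for the change in PRO score from baseline to each postdose visit for the HO population". SAP Table GBGC.5.1 defines the HO population as "A subset of the ITT population who signed an informed consent for the HO addendum and completed testing on at least 1 occasion". The dimension responses "will also be descriptively examined", with no population named in that sentence.

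**The concern.** A questionnaire collected from main-study patients for a main-study objective is modelled only in those who also consented to an optional-looking add-on. Nothing in SAP 5.18 explains why. Where addendum consent is incomplete, data already collected from children and adolescents are left out of the planned model. The estimate then loses precision and describes a narrower group than the one named in the objective.

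The silence on the dimensions adds a second problem. Through the SAP 5.16 default, they would be summarised in ITT patients with post-rescue values treated as missing. By their position in SAP 5.18, they would be summarised in the HO population. Two programmers could produce different denominators for one questionnaire completed at one sitting. SAP 5.18 also does not say whether the post-rescue rule still applies once the HO population replaces ITT.

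What is at stake is limited to the exploratory health-status results. None of them belongs to the hypotheses H1 to H12 in SAP 5.3.

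**Working it through.** The plan gives no figure for this analysis to reproduce, so the first part of the check sets the texts side by side.

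1. *Is EQ-5D-Y tied to an addendum in the main protocol?* Protocol 6.3, 7.1, 10.2 and Attachment 1 mention none for it. Where the protocol does rely on an addendum, it says so: Protocol 10.3 refers to additional samples from patients in the PK/PD addendum.
2. *What is the HO population for?* The SAP revision history describes it as a health-outcome addendum population, added in Version 4. SAP 5.18 uses it for the PedsQL Generic Core and Diabetes Module scales, which do not appear in the main protocol's objectives, measures or schedule. The likely explanation is that it was created for the addendum instruments and then extended to EQ-5D-Y. This is an inference, because the addendum itself is not available.
3. *Does SAP 5.18 override SAP 5.16?* For the VAS and index model, yes, explicitly. For the dimensions, no population is stated, so both readings remain open.

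**Size.** Let *u* be the share of patients with EQ-5D-Y data who signed the addendum. The documents do not give *u*; the values below are assumptions.

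- Standard error relative to using all patients with EQ-5D-Y data: 1/√u.
- Illustration: take the 120 planned completers (Protocol 12.1, SAP 5.1), randomised 1:1:1, so 80 on pooled dulaglutide and 40 on placebo, and assume that all of them have EQ-5D-Y data.
- Patients left out: 120(1 − u).
- Standard error of the pooled-versus-placebo difference, in SD units of the VAS change: √(1/(80u) + 1/(40u)). The 95% half-width is 1.96 times this.
- Example at u = 1: √(1/80 + 1/40) = √0.0375 = 0.194, and 1.96 × 0.194 = 0.38.

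| Assumed uptake u | 1/√u | SE increase | Patients left out of 120 | SE (SD units) | 95% half-width (SD units) |
|---|---|---|---|---|---|
| 100% | 1.000 | 0% | 0 | 0.194 | 0.38 |
| 90% | 1.054 | +5% | 12 | 0.204 | 0.40 |
| 75% | 1.155 | +15% | 30 | 0.224 | 0.44 |
| 50% | 1.414 | +41% | 60 | 0.274 | 0.54 |
| 30% | 1.826 | +83% | 84 | 0.354 | 0.69 |

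The patient counts are upper bounds at each uptake, because the translation limit means that not every completer will have EQ-5D-Y data. SAP 5.18 also reports these analyses by age, split at 13 and at 14 years, so the age-group results rest on fewer patients still.

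**The case against.** The strongest reply is that the SAP does not contradict itself. The default in SAP 5.16 yields to other statements, SAP 5.18 makes one, and choosing a population for an exploratory analysis is the sponsor's prerogative. That is right as far as it goes: this is an unexplained departure from the default and from the main-protocol objective, not an inconsistency of rules. The exception clause does not help the dimensions, for which nothing is stated.

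A second reply is that the addendum and the consent pages cannot be seen. That EQ-5D-Y is collected without addendum consent is inferred from the main protocol's silence. If nearly every patient with EQ-5D-Y data signed, the two populations almost coincide. This also stands, and it is why the size is given as a range that starts at zero. It does not argue for keeping the restriction, since under full uptake removing it costs nothing.

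Third, SAP 5.18 names no population other than HO and closes with a sentence applying the age breakdown to all of the preceding analyses, so HO is the more natural reading for the dimensions. That is fair, but the reader should not have to infer it. If HO is what is meant, the dimension summaries share the VAS model's restriction.

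Finally, SAP 5.6 summarises baseline characteristics for both the ITT and HO populations, so readers will see how the two differ. That helps interpretation but does not recover the omitted data.

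**Conclusion.** The concern holds, as a minor improvement to an exploratory analysis. As written, the VAS model excludes any patient with EQ-5D-Y data who did not sign the HO addendum, without justification, and the dimension population is left unstated.

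The cost depends entirely on an uptake figure that the documents do not give: none at full uptake, and a standard error 41% larger if half signed. The half-widths also assume that all 120 planned completers have EQ-5D-Y data, and they use a simple two-group comparison, not the planned repeated-measures model. No bias in the comparison between arms is demonstrated. The conclusion about the wording is firm; the size of the consequence is unknown.

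**What to change.** In SAP 5.18:

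- Analyse EQ-5D-Y VAS change, and the index if available, in ITT patients with a baseline and at least one post-baseline EQ-5D-Y. This agrees with SAP 5.2, which already excludes patients without post-baseline data from inferential analysis.
- Summarise the dimension responses in ITT patients with EQ-5D-Y data, and name that population.
- State that post-rescue measurements are treated as missing in both, following SAP 5.16.
- Keep the HO population for the PedsQL scales only.

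The cost is the population wording in SAP 5.18 and the matching table shells. No data collection, trial conduct or alpha allocation changes, and using all the EQ-5D-Y data collected should not cost precision.

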6.1. Interim Analyses

An independent DMC will have the responsibility to review the interim analysis results in order to monitor the safety of the patients in the study until the last patient reaches the primary endpoint at 26 weeks. The detailed analysis and communication plan for the interim analyses will be defined in a separate DMC charter. An internal SAC but external to the study team will perform the data analysis for the DMC. As no efficacy analyses are planned by the DMC, the Family-wise Error Rate (FWER) will not be affected by any of these interim analyses; hence no alpha spending is necessary.

6.1.1. Safety Analysis

The DMC will conduct a safety interim approximately every 6 months with initiation after 50 patients are enrolled into the study, as deemed appropriate based on the observed enrollment rate, until the last patient reaches the primary endpoint at 26 weeks. However, the number of interims will be determined by the enrollment rate: if enrollment is much slower than expected, safety interims may begin sooner and may occur less frequently (annually).

6.1.2. Sample Size Re-Estimation

As described in Section 5.1, a sample size re-estimation calculation may be conducted by the SAC. Based on this calculation, the SAC will recommend to the sponsor either increasing the total enrollment or making no changes to the target enrollment based on pre-specified rules. Only the SAC will be unblinded for this analysis. The only information provided to the sponsor by the SAC will be the recommended sample size.

For further details on the statistical methodology, see Section 5.1.

